2.12 Patient-reported outcomes

Summaries will be based on the FAS and will be presented separately for each treatment group.

For DLQI, missing values will be replaced by LOCF. Baseline values will not be carried forward. If no pre-treatment value exists, values obtained after first dose of treatment can be used as baseline only if it was collected on the same day as first dose. In addition, missing baseline (PROs) values will be replaced by the means or modes of non-missing baseline values stratified by age group (<65 years, 65 years and older) and sex, for continuous scale or categorical/ordinal scale, respectively.

Dermatology Life Quality Index

The DLQI measures functional disability of subjects with dermatological disorders that are greater than 18 years of age and had been utilized as a relevant clinical measure in atopic dermatitis, as well as other dermatitis clinical trials. The DLQI is a simple, validated, self-administered 10-item questionnaire. The instrument contains six functional scales (i.e., symptoms and feeling, daily activities, leisure, work and school, personal relationships, treatment). For the DLQI, each question will be answered with the following response: “not at all”, “a little”, “a lot”, or “very much”. “Not relevant” is also a valid response. Seven scores will be derived from the DLQI: the total score of each of the six dimensions as well as the total score over all items. The higher the score, the more quality of life is impaired.

For each of the seven scores, the percentage change from baseline will be derived. Summary statistics will be provided for absolute values as well as for the percentage change by visit and treatment group.

In addition, summary statistics will be provided for number of subjects achieving DLQI 0 or 1. Treatment groups will be compared by Fisher’s exact test.

Self-Injection Assessment Questionnaire (SIAQ)

All SIAQ analyses will be based on the Safety Set.

Summary statistics for the absolute values of the domain scores at Randomization (baseline) will be provided by treatment group including total for the PRE-module and the POST-module. The number and percentage of subjects in each of the 5 categories (likert scale) for each item will be presented by visit and treatment group including total.

Item and domain scores from the PRE module taken before the first self-injection at Randomization (baseline) will be compared with the corresponding item and domain scores (feeling about injections, self-confidence domains, and overall satisfaction of self-injection item) from the POST modules. Change in domain scores from PRE module will be summarized by visit and treatment group including total.

Domain scores will be calculated only if 50% or more items of the domain are completed. Missing items will not be imputed. Subjects who discontinued or who missed a visit and have the SIAQ questionnaire not completed will not be considered in the analyses at the corresponding visit.

2.13 Biomarkers

Not applicable.

[REDACTED]

2.15 Interim analysis

Week 16 primary analysis will be performed after all subjects have completed Week 16 visit. Additional analyses may be performed to support health authority interactions as necessary. At the End of Study, a final analysis of all data collected up to last study visit (Week 52) will be performed when all subjects have completed the last study visit.

Trial modifications are not planned based on any interim analysis.

3 Sample size calculation

A response rate of 8% for PASI 75 response and IGA mod 2011 0 or 1 response in the placebo group is expected, whereas a response rate of 62% for PASI 75 response and 55% for IGA mod 2011 0 or 1 is the anticipated response in the secukinumab 300 mg 2 mL auto-injector s.c. group.

Placebo-response rates between 3% and 7% have been reported in [Papp et al 2005](#), [Menter et al 2008](#), [Leonardi et al 2008](#), and [Papp et al 2008](#).

3.1 Primary endpoint (co-primary endpoint)

With respect to the co-primary endpoint (PASI 75 response and IGA mod 2011 0 or 1 response at Week 12), the type-I-error will be 2.5% one-sided for comparison. With 40 subjects per group and assuming a response rate of 8% for PASI 75 response and IGA mod 2011 0 or 1 response in the placebo group, the power to show a response rate of 62% for PASI 75 response and 55% for IGA mod 2011 0 or 1 response in the secukinumab 300 mg (2 mL auto-injector s.c.) group based on Fisher's exact test (nQuery Advisor 7.01, two group Fisher's-exact test of equal proportions) is above 99% for PASI 75 response and IGA mod 2011 0 or 1 response.

3.1.1 Secondary endpoints

The study should be sufficiently powered (above 90%) to show a response rate of 46% for PASI 90 response if the placebo rate is assumed as 8%.

4 Change to protocol specified analyses

The following analyses have been removed:

- The maximum change (maximum decrease and maximum increase) from baseline within treatment period for each laboratory parameter
- The stratified Van-Eltern testing and Hodges-Lehmann estimates for the absolute value and the percentage change from baseline of DLQI total score.

5 Appendix

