Other Secondary Objective(s) 
To assess the efficacy of secukinumab 300 mg when administered in 2 mL AI in subjects with plaque-type psoriasis with respect to PASI score, IGA mod 2011 score, PASI 50 / 75 / 90 / 100 and IGA mod 2011 0 or 1 response up to Week 12 compared to placebo, and over time up to Week 52.To investigate the clinical safety and tolerability of secukinumab 300 mg 2 mL AI as assessed by vital signs, clinical laboratory variables, and adverse events monitoring, compared to placebo.To assess the subject usability (ability to follow instructions for use and potential use-related hazards) and satisfaction with the new secukinumab 2 mL AI utilizing a self-administered SIAQ and investigator/site staff observation of secukinumab 300 mg 2 mL AI administration.To investigate the effects of secukinumab 300 mg when administered in 2 mL AI with respect to DLQI 0 or 1 achievement and DLQI changes at Week 12 compared to placebo, and over time up to Week 52.	Endpoint(s) for other secondary objective(s) 
PASI score and IGA mod 2011 score at each visit up to week 52PASI 50, PASI 75, PASI 90, PASI 100 and IGA mod 2011 0 or 1 response at each visit up to week 52Treatment emergent adverse events, change from baseline to each study visit in clinical laboratory variables and vital signsSuccessful self-injection, subject use errors, item and domain scores from the SIAQ, change in SIAQ domain scoresDLQI 0 or 1 score at each visitChange from baseline in each of the seven DLQI scores and in the DLQI total score

Objective(s)	Endpoint(s)

3 Study design

This is a multicenter, randomized, double-blind, placebo-controlled, parallel-group trial in approximately 120 subjects with moderate to severe plaque-type psoriasis.

It is expected that subjects will be enrolled at around 30 study sites worldwide.

The study consists of 3 periods:

- Screening Period (of at least 1 week and up to 4 weeks between Screening and Randomization)

The screening period is used to assess eligibility of the subjects and to taper subjects off prohibited medications.

- Treatment Period 1 (of 12 weeks, double-blind between Randomization and Week 12 pre-dose)

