1.1 Study design

This is a multicenter, randomized, double-blind, placebo-controlled, parallel-group trial in approximately 120 subjects with moderate to severe plaque-type psoriasis.

Randomization: Eligible subjects will be randomized using a 2:2:1:1 ratio into one of the following 4 treatment arms. In order to achieve a balanced weight distribution in each treatment arm, randomization in these four groups will be stratified by body weight at baseline (< 90 kg or \geq 90 kg). • Group 1: Secukinumab 300 mg (2 mL AI): one 2 mL secukinumab 300 mg AI plus two 1 mL PFS matching placebo secukinumab s.c. injections once weekly at Randomization, Weeks 1, 2, and 3, followed by dosing every four weeks, starting at Week 4 and until Week 48, except for weeks 13, 14, and 15 where subjects will self-administer two 1 mL placebo secukinumab 150 mg PFS plus one 2 mL AI matching placebo secukinumab s.c. injections.

- Group 2: Secukinumab 300 mg (2 x 1 mL PFS): two 1 mL secukinumab 150 mg PFS plus one 2 mL AI matching placebo secukinumab s.c. injections once weekly at Randomization, Weeks 1, 2, and 3, followed by dosing every four weeks, starting at Week 4 and until Week 48, except for weeks 13, 14, and 15 where they will self-administer a weekly dose of the two 1 mL placebo secukinumab 150 mg PFS plus one 2 mL AI matching placebo secukinumab s.c. injections.
- Group 3: Placebo - Secukinumab 300 mg (2 mL AI): placebo treatment administered as two 1 mL placebo secukinumab plus one 2 mL AI matching placebo secukinumab s.c. injections once weekly at Randomization, Weeks 1, 2, and 3, followed by dosing every four weeks starting at week 4 till week 8. Prior to receiving the Week 12 dose, PASI 90 response will be evaluated. PASI 90 responders will receive placebo every four weeks from week 12 till week 48, except for weeks 13, 14, and 15 subjects will self-administer a weekly dose of two 1 mL placebo secukinumab 150 mg PFS plus one 2 mL AI matching placebo secukinumab s.c. injections. The PASI 90 non-responders will be assigned to Secukinumab 300 mg (2 mL AI) group and receive their treatment every four weeks from week 12 till week 48, except for weeks 13, 14, and 15 where the patients will self-administer a weekly dose of the Secukinumab 300 mg (2 mL AI) group treatment.

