2.7 Analysis of secondary efficacy objective(s)

2.7.1 Secondary endpoints

PASI 50, PASI 75, PASI 90, PASI 100, and IGA mod 2011 0 or 1 response over time

Summary statistics for PASI 50, PASI 75, PASI 90, PASI 100, and IGA mod 2011 0 or 1 response by visit will be presented in contingency tables and will include absolute and relative frequencies. Confidence intervals for response rates will be derived as well based on the exact method.

For PASI 50, PASI 75, PASI 90, PASI 100, and IGA mod 2011 0 or 1 response at each visit, up to Week 12, comparisons between 2mL AI vs placebo and 2mL AI vs 1mL PFS x 2 will be conducted using logistic regression model with treatment group, body weight stratum and baseline PASI as effects.

For PASI 50, PASI 75, PASI 90, PASI 100, and IGA mod 2011 0 or 1 response, the placebo adjusted response rates (i.e., risk difference) including 95% confidence interval (based on normal approximation) will be derived by visit, up to Week 12. In addition, Fisher's exact test will be applied to the treatment group comparisons between 2mL AI versus placebo. In addition, the risk difference between 2ml AI group vs. 1ml PFS group, including 95% confidence interval (based on normal approximation) may be derived by visit, up to Week 52.

Figures will be provided as well displaying estimates for response rates over time by treatment including 95% confidence intervals.

PASI score over time

Summary statistics will be provided for absolute PASI scores as well as for percent change from baseline by visit and treatment group. Figure will be provided for percentage changes in PASI scores over time.

IGA mod 2011 score over time

Summary statistics for the IGA mod 2011 score over time will be presented by visit and by treatment group in contingency tables. Figures will also be provided.

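### SAP section 4 deletes the only between-arm analysis of DLQI score and replaces it with nothing, so the objective's DLQI-change comparison with placebo has no difference, confidence interval or test

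*SAP*

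**What the plan says.** **The objective.** Protocol section 2, Table 2-1, keeps a secondary objective for the 2 mL auto-injector (AI) on "DLQI 0 or 1 achievement and DLQI changes at Week 12 compared to placebo". The matching endpoints include change from baseline in the DLQI total score.

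**The protocol's analysis.** Protocol 12.6.3 planned a Van-Elteren test at each visit, stratified by questionnaire language, on the absolute value and percentage change of the DLQI total score, for secukinumab against placebo. Stratified Hodges-Lehmann estimates with confidence intervals went with it. The protocol names the Van-Elteren test as the main basis for conclusions.

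**The deletion.** SAP section 4, on changes to the protocol's analyses, lists as removed "The stratified Van-Eltern testing and Hodges-Lehmann estimates for the absolute value and the percentage change from baseline of DLQI total score".

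**What is left for DLQI score.** SAP 2.12 says: "Summary statistics will be provided for absolute values as well as for the percentage change by visit and treatment group". SAP Table 2-7 and SAP 5.4.1 agree: summary statistics only. DLQI 0/1 keeps Fisher's exact test (SAP 2.12).

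**PASI score.** The efficacy objective in Table 2-1 compares the AI with placebo up to Week 12 "with respect to PASI score, IGA mod 2011 score", and on the PASI and IGA responder endpoints. For the score, SAP 2.7.1 says: "Summary statistics will be provided for absolute PASI scores as well as for percent change from baseline by visit and treatment group". Protocol 12.6.1 already said the same.

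**The concern.** The objective asks for a comparison with placebo. The analysis that would have supplied it for DLQI change is gone, but the objective has not been altered. A study report that follows the SAP would print DLQI means and percentage changes arm by arm and leave the reader to subtract them, with no statement of precision. Any contrast produced later, for example at a health authority's request, would be post hoc, with the choice of method made after unblinding.

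DLQI 0/1 does not fill the gap. It records who reaches a threshold, not how far quality of life moves relative to placebo, and Fisher's exact test returns a p-value without an effect size.

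**Working it through.** **1. The plan's own figures.** The SAP's numerical claims concern power. SAP 3.1 sets the error level ("the type-I-error will be 2.5% one-sided for comparison") and the group size ("With 40 subjects per group and assuming a response rate of 8% for PASI 75 response"). The group size follows from SAP 1.1 ("Eligible subjects will be randomized using a 2:2:1:1 ratio") with 120 subjects and the two placebo groups pooled up to Week 12 (Protocol 6.1.3):

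- AI: 120 × 2/6 = 40
- PFS: 120 × 2/6 = 40
- placebo: 120 × (1 + 1)/6 = 40

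Full enumeration of Fisher's exact test at one-sided 2.5%, 40 per group, placebo rate 8%:

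| Endpoint | AI rate | SAP states | Recomputed |
|---|---|---|---|
| PASI 75 | 62% | above 99% | 99.97% |
| IGA 0/1 | 55% | above 99% | 99.72% |
| PASI 90 | 46% | above 90% | 97.3% |

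All three claims reproduce. None depends on DLQI or PASI score.

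**2. Which components of the two objectives have a planned comparison with placebo.**

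| Component | Between-arm analysis in protocol | Between-arm analysis in SAP |
|---|---|---|
| DLQI change or score | Van-Elteren; Hodges-Lehmann with CI (12.6.3) | none (section 4, 2.12, Table 2-7, 5.4.1) |
| DLQI 0/1 | Fisher (12.6.3) | Fisher (2.12) |
| PASI score | none (12.6.1) | none (2.7.1, 5.4.1) |
| PASI 50/75/90/100 and IGA 0/1 response | logistic regression (12.6.1) | logistic regression odds ratios; risk differences with 95% CI by visit to Week 12 (2.7.1, 5.4.3) |

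SAP 2.5.3 does give 95% intervals for multiply imputed PASI means, but these describe single arms and not a difference. Only the first row loses something between protocol and SAP.

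**3. What a restored DLQI estimate would deliver.** For an unadjusted difference in means with complete data:

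half-width = t(0.975, 78) × SD × √(1/40 + 1/40) = 1.991 × 0.2236 × SD = 0.445 SD

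The documents give no SD for DLQI change, so it is assumed:

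| Assumed SD (points) | 4 | 5 | 6 | 7 | 8 |
|---|---|---|---|---|---|
| 95% half-width (points) | 1.8 | 2.2 | 2.7 | 3.1 | 3.6 |

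The DLQI total runs from 0 to 30. At two-sided 5%, power is 61% for a standardised difference of 0.5, 83% for 0.65, 95% for 0.8 and 99% for 1.0. The trial is large enough to give an informative interval.

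**The case against.** The removal is declared where a reader would look for it, so this is not a hidden contradiction. The endpoints lie outside the H1 to H3 sequence, and SAP 2.7.2 marks hypothesis and model as not applicable for the secondary efficacy endpoints. A sponsor may choose to describe secondary outcomes only. All of that stands. It means that no confirmatory claim is affected, but not that a comparison named in an objective can go without an estimate.

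A reader might infer that two whole objectives end with no treatment-difference estimate. The documents do not support that. The efficacy objective keeps odds ratios and risk differences with intervals for its responder components. The DLQI objective keeps Fisher's exact test for DLQI 0/1. It may also keep a risk difference: SAP 5.4.2 promises one for response variables, and SAP 2.5.3 counts DLQI 0/1 as such, though the examples in 5.4.2 do not name it.

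A reader might also infer that the SAP dropped a PASI-score comparison. It did not, because the protocol never had one. The four PASI response levels are cut-points of change in the same score and are all compared with placebo at each visit up to Week 12. The case for a PASI mean difference is therefore weaker than the case for DLQI.

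On method, the deleted DLQI analysis was rank-based, so ANCOVA is not the only reasonable replacement. DLQI uses last observation carried forward, and missing baselines are filled with a mean or mode (SAP 2.12). A model fitted to such data ignores imputation uncertainty. At Week 12 this should matter little: baseline is not carried forward, and Protocol Table 8-1 appears to schedule no DLQI between baseline and Week 12.

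**Conclusion.** The concern holds for one component and in part for a second. As the SAP stands, DLQI change at Week 12 against placebo has no difference, interval or test, although the objective still asks for the comparison and the protocol had an analysis for it. PASI score also has no between-arm estimate, but that gap was inherited from the protocol and the responder analyses partly cover it.

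The missing DLQI interval would have a half-width of about 0.445 SD, or 2.7 to 3.6 points for an SD of 6 to 8. This assumes 40 analysed per arm, complete data and no covariate adjustment, and the SD is an assumption. No figure is put on the precision that baseline adjustment would add: the documents give no baseline-to-Week 12 correlation, and neither plans a raw change-score contrast to measure it against. Type I error control and the stated power are unaffected. The change is worth making because the trial can answer the question with data already collected.

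**What to change.** **SAP 2.12 (main change).** Prespecify the Week 12 AI minus placebo difference in change from baseline in DLQI total score, with a two-sided 95% confidence interval. Choose one method now: ANCOVA with treatment, baseline DLQI and weight stratum, or the protocol's Hodges-Lehmann estimate reinstated. Amend SAP section 4 and Table 2-7 to match, and state in section 4 why the Van-Elteren test was dropped if it stays out.

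**SAP 5.4.2 (one sentence).** Say whether the placebo-adjusted risk difference with its interval applies to DLQI 0/1.

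**SAP 2.7.1 (optional).** Add an ANCOVA of change in PASI score, with treatment, baseline PASI and weight stratum, at visits up to Week 12. Change in PASI is already imputed in 100 data sets under SAP 5.4.4, so the model can be fitted in each and pooled by Rubin's rules.

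Label every added estimate as nominal and outside H1 to H3. Rewording the DLQI component as descriptive would remove the mismatch, but would leave the question unanswered.

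**Cost.** SAP wording and a few extra tables. No new data, no change to sample size and no effect on the confirmatory tests.

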5.1 Imputation rules

5.1.1 Study drug

Any partial dates will be imputed as follows:

We take the earlier day of

- The last day in the month and
- The calculated end day of the corresponding epoch

5.1.2 AE date imputation

Impute AE end date:

1. If the AE end date ‘month’ is missing, the imputed end date should be set to the earliest of the (min (last visit date, last dose date + 84 days), 31DECYYYY, date of death).
2. If the AE end date ‘day’ is missing, the imputed end date should be set to the earliest of the (min (last visit date, last dose date + 84 days), last day of the month, date of death).
3. If AE ‘year’ is missing or AE is ongoing, the end date will not be imputed.

Impute AE start date:

Before imputing AE start date, find the AE start reference date.

1. If the (imputed) AE end date is complete and the (imputed) AE end date < treatment start date then AE start reference date = min(informed consent date, earliest visit date).
2. Else AE start reference date = treatment start date

1. If the AE start date ‘year’ value is missing, the date uncertainty is too high to impute a rational date. Therefore, if the AE year value is missing, the imputed AE start date is set to NULL.

2. If the AE start date 'year' value is less than the treatment start date year value, the AE started before treatment. Therefore:
 - a. If AE 'month' is missing, the imputed AE start date is set to the mid-year point (01JulYYYY).
 - b. Else if AE 'month' is not missing, the imputed AE start date is set to the mid-month point (15MONYYYY).
3. If the AE start date year value is greater than the treatment start date year value, the AE started after treatment. Therefore:
 - a. If the AE month is missing, the imputed AE start date is set to the year start point (01JanYYYY).
 - b. Else if the AE month is not missing, the imputed AE start date is set to the later of (month start point (01MONYYYY), AE start reference date + 1 day).
4. If the AE start date year value is equal to the treatment start date year value:
 - a. And the AE month is missing the imputed AE start date is set to the AE reference start date + 1 day.
 - b. Else if the AE month is less than the treatment start month, the imputed AE start date is set to the mid-month point (15MONYYYY).
 - c. Else if the AE month is equal to the treatment start date month or greater than the treatment start date month, the imputed AE start date is set to the later of (month start point (01MONYYYY), AE start reference date + 1 day).

If complete (imputed) AE end date is available and the imputed AE start date is greater than the (imputed) AE end date, then imputed AE start date should be set to the (imputed) AE end date.

5.1.3 Concomitant medication date imputation

Impute CM end date:

1. If CM end day is missing and CM month/year are non-missing then impute CM day as the minimum of treatment end date and the last day of the month.
2. If CM end day/month are missing and CM year is non-missing then impute CM day as the minimum of treatment end date and the end of the year (31DECYYYY).

3. If imputed CM end date is less than the CM start date, use the CM start date as the imputed CM end date.

Impute CM start date:

1. If the CM start date year value is missing, the imputed CM start date is set to one day prior to treatment start date.

2. If the CM start date year value is less than the treatment start date year value, the CM started before treatment. Therefore:

a. If the CM month is missing, the imputed CM start date is set to the mid-year point (01JulYYYY).

b. Else if the CM month is not missing, the imputed CM start date is set to the mid-month point (15MONYYYY).

3. If the CM start date year value is greater than the treatment start date year value, the CM started after treatment. Therefore:

a. If the CM month is missing, the imputed CM start date is set to the year start point (01JanYYYY).

b. Else if the CM month is not missing, the imputed CM start date is set to the month start point (01MONYYYY).

4. If the CM start date year value is equal to the treatment start date year value:

a. And the CM month is missing or the CM month is equal to the treatment start date month, then the imputed CM start date is set to one day prior treatment start date.

b. Else if the CM month is less than the treatment start date month, the imputed CM start date is set to the mid-month point (15MONYYYY).

c. Else if the CM month is greater than the treatment start date month, the imputed CM start date is set to the month start point (01MONYYYY).

If complete (imputed) CM end date is available and the imputed CM start date is greater than the (imputed) CM end date, then imputed CM start date should be set to the (imputed) CM end date.

